### 2.3. Study Schedule

Table 1 presents the schedule of study visits and assessments.

**Table 1: Schedule of Events**

Study Day	Study Specific Screen	Inpatient Period									Outpatient Visit	Phone Call
		-1	1	2	3	4	5	6	7	8		
Informed Consent and Comprehension Test	X											
Demographics	X											
Inclusion/Exclusion Criteria	X	X	X									
Medical History	X	X										
Functional Bowel Survey	X											X
Full Physical Exam	X	X										

**RESTRICTED**

	SPONSOR: Scandinavian Biopharma Holding AM (SBH)	PROTOCOL NUMBER: OEV-131	PROTOCOL TITLE: Pre-Study of wild type Enterotoxigenic E.coli (ETEC) Strain for Verification of a planned Challenge Dose	VERSION NO: 1.0
				VERSION DATE: 14JUN2024

Study Day	Study Specific Screen	Inpatient Period									Outpatient Visit	Phone Call
		-1	1	2	3	4	5	6	7	8		
Focused Physical Exam			X	X	X	X	X	X	X	X	(X) 	
Vital Signs 	X	X	X	X	X	X	X	X	X	X	X	
Serology (HIV, HBsAg, and HCV)	X 											
Hematology	X	X 										
Clinical Chemistry	X	X 										
IgA deficiency screen	X 											
Serum HCG Pregnancy Test 	X	X										
Urine Drug Screen	X											
Urine Pregnancy Test 			(X)								X	
Enrollment			X									
E24377A challenge			X									
Prior and concomitant medications	X	X	X	X	X	X	X	X	X	X	X	
Interim Medical Interview 			X	X	X	X	X	X	X	X	X	X
AE			X	X	X	X	X	X	X	X	X	X
SAE/AESI			X	X	X	X	X	X	X	X	X	X
Antibiotic therapy								X 	X	X		
Stool collection for weighing and grading 			X	X	X	X	X	X	X	X		
Stool culture			X	X 	X	X 	X	X	X	X		
Serum Sample for Immunogenicity		X	(X) 	X	X					X		X
Whole blood for ALS	X	(X) 		X					X			
Fecal sample for immunogenicity	X	(X) 	X	X	X				X	X		X
Follow-Up Telephone Contact												X
ETEC Impact on ADLs								X				

Note: (X) denotes optional event or procedure

Physical exam on Day 29 optional if there are symptoms.

Pulse, sitting, lying or standing blood pressure and temperature will be measured at least 3 times daily starting on Day 1. In addition, postural blood pressure and pulse will be measured if suspicion or evidence of hypovolemia (based on assessment by clinician). Vital signs may be measured more frequently if the subject is ill.

Must be collected from Day -30 to Day -2

Hematology and clinical chemistry will be performed at Day -1 if not performed within the previous 7 days.

Serum HCG pregnancy tests will be performed for people of child-bearing potential. Urine HCG will be done if serum results from admission day (Day -1) are not available.

During the inpatient and outpatient phases of the study, the interview will be used to update baseline medical history, monitor safety, and to confirm ongoing eligibility.

Subjects meeting the criteria for early antibiotic treatment per the discretion of an investigator may start this treatment prior to Day 6.

Weighing and grading ends once subject has two consecutive ETEC negative cultures, unless there is a clinical indication to continue.

Quantitative stool cultures (cfu per gram of stool) will be collected on Days 2 and 4.

To be collected before challenge if not taken on Day -1.

**RESTRICTED**

	SPONSOR: Scandinavian Biopharma Holding AM (SBH)	PROTOCOL NUMBER: OEV-131	PROTOCOL TITLE: Pre-Study of wild type Enterotoxigenic E.coli (ETEC) Strain for Verification of a planned Challenge Dose	VERSION NO: 1.0

## 2.4. Statistical Considerations for the Study Design

### 2.4.1. Sample Size Considerations

In preparation for a planned phase 3 vaccination and CHIM study, it is assumed based on previous clinical experience, that a pre-study in up to 30 subjects should be sufficient to estimate the incidence of moderate and severe diarrhea among subjects challenged with 4x109 cfu of the *E. coli* E24377A strain. With 25 subjects and an attack rate of 60% or 72%, the 95% Clopper-Pearson confidence interval for the estimated incidence would be (0.39, 0.79) or (0.51, 0.88), respectively.

Since there is a maximum capacity of 30 subjects for the in-patient period, the number of subjects will not exceed 30.

### 2.4.2. Allocation of Subjects to Study Arms

Not applicable, as this is a single-arm study.

### 2.4.3. Blinding

Not applicable, as this is an open label study.

## 2.5. Study Definitions and Derived Variables

### 2.5.1. Diarrhea

Each stool will be graded according to the following scale:

- Grade 1 = firm, formed
- Grade 2 = soft but still formed
- Grade 3 = thick liquid
- Grade 4 = thin liquid
- Grade 5 = clear or translucent, watery

A loose stool is defined as a grade 3-5 stool.

Diarrhea is defined as passing at least 2 loose (grade 3-5) stools within a 24-hour period. Diarrhea severity is assigned according to the following scale:

Mild	2-3 grade 3-5 stools in 24 hours and $\leq$ 400 grams of grade 3-5 stools passed in a 24-hour period
Moderate	4-5 grade 3-5 stools in 24 hours or $>$ 400-800 grams of grade 3-5 stools passed in a 24-hour period
Severe	$\geq$ 6 grade 3-5 stools in 24 hours or $>$ 800 grams of grade 3-5 stools passed in a 24-hour period

A diarrhea episode starts when the first grade 3-5 stool that contributes to diarrhea of any severity is passed. A diarrhea episode ends when a subject has not passed any grade 3-5 stools within the preceding 24 hours. A rolling 24-hour window will be used to determine the severity of diarrhea. At the time of each grade 3-5 stool passing, all grade 3-5 stool output during the previous 24 hours will be assessed against the diarrhea severity scale, and a severity will be assigned to that 24-hour window. Due to this rolling window, multiple 24-hour windows may be assessed, and multiple diarrhea severity thresholds may be met during a single diarrhea episode. The maximum severity of diarrhea met during a diarrhea episode will be considered the severity of that episode.

**RESTRICTED**

DOCUMENT REF.: SOP-ST-01 LAST REVISION DATE: N/A VERSION NO.: 1.0	DOCUMENT NAME: Statistical Analysis Plan			
	SPONSOR: Scandinavian Biopharma Holding AM (SBH)	PROTOCOL NUMBER: OEV-131	PROTOCOL TITLE: Pre-Study of wild type Enterotoxigenic E.coli (ETEC) Strain for Verification of a planned Challenge Dose	VERSION NO: 1.0
				VERSION DATE: 14JUN2024

## 2.5.2. Primary Endpoint

An adjudication committee will determine whether each subject has met the primary endpoint. Primary endpoint determinations for each subject will be based on the majority vote of the adjudication committee as described in the adjudication charter.

## 2.5.3. Unadjudicated Primary Endpoint

The unadjudicated primary endpoint, defined only by objective stool output criteria without adjudicator input, will be assessed as a sensitivity analysis. The unadjudicated primary endpoint is defined as  $\geq 4$  grade 3-5 stools or  $> 400$  grams of grade 3-5 stools passed within a rolling 24-hour period. Diarrhea episodes beginning any time after challenge through 120 hours post-challenge may contribute toward the unadjudicated primary endpoint.

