7.3.2 Risks

Risks Associated with ETEC Infection: The main risk is also the primary objective in this study: diarrhea caused by ETEC. Infection with ETEC can cause profuse watery diarrhea, abdominal cramping, abdominal pain, malaise, headache, urgency of defecation, lightheadedness and/or dehydration. Fever, nausea with or without vomiting, chills, loss of appetite, muscle aches and bloating can also occur but are less common. Illness develops 1-3 days after exposure and usually lasts 3-4 days [29] without treatment, but generally improves within 24 hours of antibiotic therapy.

In order to reduce the risk of secondary infection after discharge, all subjects in the study will receive a 3-day course of antibiotics starting no later than Day 6. Ciprofloxacin is the first-line antibiotic treatment for all subjects. If a subject is unable or unwilling to take ciprofloxacin, azithromycin or amoxicillin will be used instead. The risk of diarrhea complications will be minimized by a conservative approach to timing of antibiotic administration, well within an interval that has been shown to be efficacious, as well as daily clinical monitoring. Stool output will be closely monitored.

Risks Associated with Post-Infectious Irritable Bowel Syndrome (PI-IBS): Recent studies also suggest an increased risk of post-infectious irritable bowel syndrome (PI-IBS) following bacterial enteritis, and infection with ETEC has been found to be associated with these sequelae. A long duration (>2 weeks) of TD has been shown to be a risk factor for development of PI-IBS [30]. Prompt treatment of the ETEC infection, as done in the present study, cuts the duration of

any ETEC illness short and thus most likely eliminates the risk of PI-IBS. Symptoms of PI-IBS will be screened for with the Functional Bowel Disorder Survey (FBS) administered on study day 180. A study provider will review each FBS. Any participant identified as having a risk for PI-IBS will be referred for follow-up care. PI-IBS may be detected in 3-17% of people who experience travelers diarrhea (TD) [9], however there have been no documented cases of PI-IBS in enteric challenge study participants [31].

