9.4.8.2 Concomitant therapy during the study

During the study, all subjects will receive a 3-day course of antibiotics.

On the morning of Day 6 (or sooner if the subject met the criteria for early antibiotic treatment; see below), all subjects will start a 3-day course of ciprofloxacin 500 mg BID.

Subjects with an allergy to or who are unwilling to take a fluoroquinolone, may receive azithromycin 500 mg by mouth daily for three days or amoxicillin 500 mg by mouth three times daily for three days.

If, because of illness, a subject is unable to take oral antibiotics, intravenous antibiotics may be given at an appropriate dose based on weight and clinical status.

Criteria for early antibiotic treatment

Subjects meeting any of the following criteria before Day 6 will start antibiotic treatment at that time:

- Severe diarrhea as defined as >800 grams of grade 3-5 stools within a rolling 24 hour-period (see Section 9.5.3.1.2).
- Stool output consistent with moderate diarrhea for 48 hours
- Diarrhea of any severity AND 2 or more of the following symptoms: severe abdominal pain, severe abdominal cramps, severe nausea, severe headache, severe myalgias, severe arthralgia), any fever ($\geq 100.4^{\circ}\text{F}$, 38.0°C), or any vomiting
- Any fever $\geq 102.1^{\circ}\text{F}$ (39.0°C)
- A study clinician determines early treatment is warranted for any other reason

Subjects who meet the criteria for early antibiotic treatment, may be discharged from the in-patient unit earlier than anticipated upon meeting discharge criteria. Discharge criteria include at least 2 stools negative for the challenge organism, having taken at least 2 doses of antibiotics, and have no or improved symptoms.

Subjects taking any other non-antibiotic medication on a chronic basis may continue with that medication unless directed otherwise by a study clinician. All such medication will be collected on admission to the inpatient facility and will be dispensed by study staff until discharge.

Rehydration

Subjects passing grade 3-5 stools post-challenge will be asked to drink liquids, at the same volume as their stool output.

A subject may be administered IV fluids if they:

- Experience abrupt onset of diarrhea, defined as passage of an initial loose/liquid stool of >300 g, or >400 g of loose/liquid stools over 2 hours in conjunction with other symptoms, as determined by PI or designee.

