### 2.5.4.2. Time to Unadjudicated Primary Endpoint

Time to meeting the unadjudicated primary endpoint is defined as the number of hours between challenge and the first grade 3-5 stool that passes the frequency or weight threshold of moderate diarrhea and occurs within a diarrhea episode that began prior to 120 hours post challenge. Subjects who did not meet the unadjudicated primary endpoint will be censored at 120 hours post challenge.

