### 2.6.4. Early Antibiotic Treatment

On the morning of Day-6, all subjects will start a 3-day course of antibiotics except those who meet at least one of the criteria for early antibiotic treatment, which include the following:

- Severe diarrhea as defined as >800 grams of grade 3-5 stools within a rolling 24 hour-period.
- Stool output consistent with moderate diarrhea for 48 hours.
- Diarrhea of any severity AND 2 or more of the following symptoms: severe abdominal pain, severe abdominal cramps, severe nausea, severe headache, severe myalgias, severe arthralgia), any fever (≥ 100.4°F, 38.0°C), or any vomiting.
- Any fever ≥ 102.1°F (39.0°C).
- A study clinician determines early treatment is warranted for any other reason.

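### The stool-only sensitivity endpoint counts subjects treated early, below the threshold, as non-events, and no planned output isolates them

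*SAP*

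**What the plan says.** Table and listing numbers here are those on the SAP mock-ups.

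- **Role of the endpoint.** SAP 2.5.3 sets up an unadjudicated primary endpoint, "defined only by objective stool output criteria without adjudicator input, will be assessed as a sensitivity analysis". It requires at least 4 grade 3-5 stools, or more than 400 g of them, in a rolling 24 hours, in an episode beginning by 120 hours.
- **Early antibiotics.** Protocol 9.4.8.2 and SAP 2.6.4 list the same five criteria. One is "Diarrhea of any severity AND 2 or more of the following symptoms"; another is "A study clinician determines early treatment is warranted for any other reason". SAP 2.6.4 starts treatment when a criterion is met. A footnote to the schedule of events words this as an option for the investigator. Either way, treatment can precede the threshold.
- **Expected effect.** Protocol 7.3.2 says that illness "generally improves within 24 hours of antibiotic therapy".
- **Time to event.** SAP 2.5.4.2: "Subjects who did not meet the unadjudicated primary endpoint will be censored at 120 hours post challenge". Nothing changes at antibiotic start.
- **Primary endpoint.** SAP 2.5.4.1 foresees that the committee may accept subjects whose stools stayed below the thresholds. It dates their event at antibiotic administration, or at 120 hours in a sensitivity analysis.
- **Outputs.** Table 12 gives both rates. Table 18 gives one overall count of early antibiotics. Table 14 pools stool totals over all subjects. Listing 6 has stool times and both endpoint decisions but no antibiotic time. Listing 10 gives the medication start day only.

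**The concern.** The study is open-label and single-arm, and a committee decides its primary endpoint. The unadjudicated rate is the planned check on that judgement. If treatment stops some illnesses before the threshold, the check errs in one direction. When the two rates differ, the reader cannot tell whether treatment pre-empted the threshold or the committee used its latitude. When they agree, treated subjects left as non-events in both rows stay invisible.

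The 120-hour stool totals have the same problem: an early-treated subject's shortened illness is averaged with full untreated courses. A footnote to the SAP schedule also lets weighing and grading end after two negative cultures, so output after treatment may not be recorded to 120 hours.

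The comparison with earlier trials adds to this. The 60-81% rates in Protocol Tables 2 and 3 counted mild diarrhea with moderate to severe gastrointestinal symptoms as illness. That group overlaps with those who can be treated early here, and the stool-only endpoint leaves it out.

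**Working it through.** **1. Can treatment precede the threshold?** Each criterion in SAP 2.6.4 is set against at least 4 stools or more than 400 g:

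| Criterion | Threshold already met? |
|---|---|
| More than 800 g in 24 h | Yes |
| "Stool output consistent with moderate diarrhea for 48 hours" | Yes |
| Diarrhea of any severity plus two listed symptoms | Not necessarily: mild diarrhea is 2-3 stools and at most 400 g |
| Fever of 39.0 °C or more | No stool requirement |
| Clinician decision | No stool requirement |

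For example, a subject with 3 loose stools totalling under 400 g, one vomit and severe cramps qualifies for treatment and is below the threshold. If output then subsides, that subject is a non-event. A subject who reaches the threshold after starting antibiotics still counts as an event, so only those who never reach it matter.

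**2. The SAP's own intervals.** Clopper-Pearson limits for x events in n subjects are Beta⁻¹(0.025; x, n−x+1) and Beta⁻¹(0.975; x+1, n−x).

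- 15/25 = 60%: (0.387, 0.789). SAP 2.4.1 gives (0.39, 0.79).
- 18/25 = 72%: (0.506, 0.879). SAP 2.4.1 gives (0.51, 0.88).

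Both are reproduced.

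**3. Size.** Let k be the number of subjects treated before Day 6 and below the threshold, with diarrhea at antibiotic start, who never reach the threshold. The documents do not give k; the values below are assumptions. The planned rate is x/n and the bound is (x+k)/n. Each subject moves it by 1/25 = 4.0 points or 1/30 = 3.3 points.

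| k | n = 25, x = 15 | 95% CI | n = 30, x = 18 | 95% CI |
|---|---|---|---|---|
| 0 | 60% | 0.387, 0.789 | 60% | 0.406, 0.773 |
| 1 | 64% | 0.425, 0.820 | 63.3% | 0.439, 0.801 |
| 2 | 68% | 0.465, 0.851 | 66.7% | 0.472, 0.827 |
| 3 | 72% | 0.506, 0.879 | 70% | 0.506, 0.853 |

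At n = 25, three subjects span the SAP's two planning rates.

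**4. What Table 12 can reveal.** Let a be sub-threshold subjects whom the committee accepts, and b threshold-meeting subjects whom it rejects. The adjudicated count minus the unadjudicated count is a − b. With a = b = 2 (illustrative), the difference is 0 although four subjects were reclassified. Treated sub-threshold subjects whom the committee leaves as non-events enter neither a nor b.

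**5. Kaplan-Meier.** Under SAP 2.5.4.2 nobody is censored before 120 hours, so the curve at 120 hours equals the crude proportion with an event by then. It gives no separate information on these subjects.

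**The case against.** **The primary rate is the adjudicated one.** This stands. A reader might infer that the study's headline attack rate is biased downward. The documents do not support that: SAP 2.5.4.1 lets the committee count sub-threshold subjects. The adjudication charter is not among the documents, so how it weighs early antibiotics cannot be checked either way.

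**The outputs are not silent.** This stands in part. Table 12 shows both rates, and Table 15 and Figures 2 and 3 show both endpoints and the alternative timing. Listings 6 and 10 together identify most such subjects to the day. It would be wrong to say that nothing bears on the size. What is missing is a count, and a clock time to order dose and stool within a day.

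**Earlier trials do not show that it is common.** This stands. Protocol Table 3 gives early antibiotics in 12/15 (80%) and 8 (50%), which invites the inference that pre-emption is frequent. The 12/15 comes from a trial of 20 subjects, and its denominator equals that trial's 15 moderate or severe cases. It therefore appears to be a share of cases; over all 20 it would be 12/20 = 60%. Neither figure says how often treatment came before the threshold.

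**The rate under the protocol's own treatment rules is a legitimate target.** This also stands. Censoring at 120 hours does not assert that a subject was untreated, and the phase 3 treatment rules are not in the documents. The understatement is relative to untreated illness only. This argues for showing both figures, not for replacing one.

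**Conclusion.** The concern holds for the unadjudicated rate, its time-to-event analysis and the pooled 120-hour stool totals. Each can be lowered by early treatment, and no planned table separates subjects whose illness was pre-empted from those who did not become ill enough. It is not shown for the adjudicated primary rate.

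The size rests on an unknown count. From 15/25, one to three such subjects mean at most 4 to 12 points, reached only if all of them would otherwise have met the threshold. With none, nothing changes, and a reported zero would itself be informative. This is an inexpensive improvement to the readout, not a flaw that invalidates the study.

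**What to change.** 1. **Table 12, count.** Add the number of subjects who started antibiotics before Day 6, before meeting the stool threshold, and did not meet it afterwards, cross-classified by adjudicated outcome. The Day 6 limit is essential: all subjects start antibiotics by then, so without it nearly every non-event would qualify and any bound would approach 100%.
2. **Table 12, bound.** Add a supplementary rate that counts as events those of them who had diarrhea (at least 2 grade 3-5 stools in 24 hours) at antibiotic start, with its Clopper-Pearson interval. Label it an upper bound for the stool-based rate only. It takes subjects without diarrhea at antibiotic start as non-events, and the footnote should say so.
3. **Listing 6.** Add the time of first antibiotic dose relative to challenge.
4. **Table 14.** Show the 120-hour totals also by early-antibiotic status.

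Table 12, Table 14 and Listing 6 are marked for the topline report (SAP 8.1) and Table 18 is not, so these additions would also bring early antibiotic use into the topline results.

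While editing, reconcile the censoring rules: SAP 2.5.4.1 censors primary-endpoint non-events at 120 hours, but the Table 15 note says 120 hours or discharge, whichever is first.

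**Cost.** SAP wording, a few table rows and one listing column. No new data should be needed: stool times are recorded to the minute (SAP 2.6.1), and SAP 2.5.4.1 and the Table 19 footnote already depend on dose timing. The drawbacks are small cells in Table 14 and a bound that includes some subjects who would never have progressed. Treatment criteria are unchanged.

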## 2.5.4. Time to Event

### 2.5.4.1. Time to Primary Endpoint

The secondary clinical endpoint, time to meeting the primary endpoint, is defined as the number of hours between challenge and the first grade 3-5 stool that passes the frequency or weight threshold of moderate diarrhea, occurs within a diarrhea episode that began prior to 120 hours post challenge, and is deemed attributable to ETEC by an adjudication committee. Subjects who did not meet the primary endpoint will be censored at 120 hours post challenge.

Some subjects whose measured stools did not meet the frequency or weight thresholds for moderate or severe diarrhea may still meet the primary endpoint according to the adjudication committee. In the time to primary endpoint analysis, such subjects will be considered to have met the primary endpoint at time of antibiotic administration. As a sensitivity analysis, these subjects will be considered to have met the primary endpoint at 120 hours post challenge.

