9.3.4 Number of subjects

Up to 30 (minimum 25) healthy subjects will be enrolled in the study. Since there is a maximum capacity of 30 subjects for the in-patient period, the number of subjects who receive the

Confidential

28 (67)

Template Version:30MAR2020

(App 1 SOP EtC1011)

E24377A strain will not exceed 30; however, additional alternate subjects may be recruited to fill in for subjects who are ineligible or chose to leave prior to challenge receipt.

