9.3.8 Removal of subjects from therapy or assessment

Subjects are free to discontinue their participation in the study at any time and for whatever reason without affecting their right to an appropriate follow-up investigation or their future care.

Subjects may be discontinued from the study at any time at the discretion of the Investigator for any of the following reasons:

- Severe non-compliance to the CSP procedures, as judged by the Investigator and/or SBH
- Subject is lost to follow-up (at least 3 attempts will be made to contact them, then a certified letter will be sent to their last known address)
- Significant AEs posing a risk for the subject, as judged by the Investigator and/or SBH

The primary reason for withdrawal / discontinuation must be specified in the eCRF and medical records.

After administration of E24377A, the subject will be encouraged to remain in the in-patient unit for the protocol-specified period (i.e., until they meet discharge criteria of 2 stools negative for challenge; see Section 9.4.8.2) and return for the scheduled out-patient study site visit on Day 29, and be available for a final contact by phone approximately 6 months after challenge. Furthermore, subjects will be encouraged to take the full course of antibiotics in order to reduce the risk of secondary infection after discharge.

If a subject expresses interest in withdrawing from the study after E24377A administration but before completion of the in-patient period, then the subject will be started on antibiotic therapy and encouraged to remain in the in-patient unit until they are no longer infected, as determined by negative stool culture. If the participant is amendable to returning for any or all in-person outpatient visits, they will be considered “off treatment” but not terminated from the study.

However, if the subject elects to withdraw from the study immediately, then the subject will receive a single dose of ciprofloxacin 500 mg prior to discharge from the in-patient unit and be provided with the remaining 5 doses of ciprofloxacin 500 mg twice daily (BID). They will be encouraged to bring stools samples in to ensure clearance of the challenge organism.

If a subject terminates the study before Day 29, every effort will be made to have the subject undergo the procedures as described in Section 9.5.6.4 for the follow-up visit.

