9.7.2 Analysis of Clinical and Microbiology endpoints

For the primary endpoint, the proportion of subjects with moderate and severe diarrhea (defined as ≥ 4 grade 3-5 stools **or** > 400 grams of grade 3-5 stools passed in a rolling 24-hour period), deemed attributable to ETEC by an adjudication committee, will be presented with point estimate and the corresponding two-sided 95% confidence interval. For secondary clinical and microbiology endpoints, descriptive statistics will be presented, including two-sided 95% confidence intervals where applicable. For time to event analysis (time to onset of diarrhea and time to primary endpoint) Kaplan-Meier time to event methods will be used.

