### 2.5.4.3. Time to Diarrhea Onset

The secondary clinical endpoint, time to onset of diarrhea, is defined as the number of hours between challenge and the first grade 3-5 stool of a subject's first diarrhea episode during the inpatient period. Subjects who experienced no diarrhea episodes during the inpatient period will be censored at 120 hours post challenge.

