### 3.5. Handling of Missing Data

All attempts will be made to collect all data per protocol. As missing data are expected to be minimal, no imputation will be performed for missing values. Any data point that appears to be erroneous or inexplicable based on clinical judgment will be investigated.

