## 14.2 Clinical Data

**Table 12: Number and Percentage of Subjects Meeting the Primary Endpoint and Unadjudicated Primary Endpoint - Full Analysis Set\***

Endpoint Type	All Subjects (N=X)		
	n	%	95% CI a
Primary Endpoint	x	xx	xx.x, xx.x
Unadjudicated Primary Endpoint	x	xx	xx.x, xx.x

Notes: N = Number of subjects in the Full Analysis Set; n = Number of subjects meeting the corresponding endpoint.

a Exact binomial confidence interval calculated via Clopper-Pearson methodology.

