**RESTRICTED**

	SPONSOR: Scandinavian Biopharma Holding AM (SBH)	PROTOCOL NUMBER: OEV-131	PROTOCOL TITLE: Pre-Study of wild type Enterotoxigenic E.coli (ETEC) Strain for Verification of a planned Challenge Dose	VERSION NO: 1.0

Notes: N = Number of subjects in the Full Analysis Set.

a Time to primary endpoint is defined as the number of hours from challenge to first grade 3-5 stool that meets at least moderate severity criteria, occurs within a diarrhea episode that began prior to 120 hours post challenge, and is deemed attributable to ETEC by an adjudication committee. Subjects who met the primary endpoint according to the adjudication committee but whose stools did not meet the frequency or weight thresholds for moderate or severe diarrhea will be considered to have met the primary endpoint at time of antibiotic administration.

b Time to primary endpoint for the sensitivity analysis is defined as the number of hours from challenge to first grade 3-5 stool that meets at least moderate severity criteria, occurs within a diarrhea episode that began prior to 120 hours post challenge, and is deemed attributable to ETEC by an adjudication committee. Subjects who met the primary endpoint according to the adjudication committee but whose stools did not meet the frequency or weight thresholds for moderate or severe diarrhea will be considered to have met the primary endpoint at 120 hours post challenge.

c Time to unadjudicated primary endpoint is defined as the number of hours between challenge and the first grade 3-5 stool that passes the frequency or weight threshold of moderate diarrhea and occurs within a diarrhea episode that began prior to 120 hours post challenge.

d Time to diarrhea onset is defined as the number of hours from challenge to first grade 3-5 stool of a subject's first diarrhea episode during the inpatient period.

e Estimated time to event is based on the survival function calculated via Kaplan-Meier methodology. Subjects who did not meet the primary endpoint will be right censored at 120 hours post-challenge or time of discharge from the inpatient unit, whichever is first. Subjects who experienced no diarrhea episodes during the inpatient period will be right censored at the time of discharge from the inpatient unit.

f Confidence intervals are calculated via log-log transformation.

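### The SAP gives incompatible censoring rules for its time-to-event endpoints, and no stated rule for classifying event-free subjects observed for less than 120 hours

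*SAP*

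**What the plan says.** **Time-to-event endpoints.**
- Primary endpoint: SAP 2.5.4.1 states "Subjects who did not meet the primary endpoint will be censored at 120 hours post challenge". SAP 2.5.4.2 repeats the 120-hour rule for the unadjudicated version. Footnote e of the Table 15 mock-up has primary-endpoint non-events "right censored at 120 hours post-challenge or time of discharge from the inpatient unit, whichever is first", and does not mention the unadjudicated version separately.
- Diarrhea onset: SAP 2.5.4.3 states "Subjects who experienced no diarrhea episodes during the inpatient period will be censored at 120 hours post challenge". Footnote e censors these subjects at discharge, which is routinely Day 9. Section 2.5.4.3 also takes as the event the first episode at any time in the inpatient period, not only within 120 hours.

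**Ways in which observation can end early.**
- Protocol 9.3.8 provides for the case where "if the subject elects to withdraw from the study immediately" after challenge.
- Protocol 9.4.8.2 allows earlier discharge after early antibiotics. Some of its early-treatment criteria do not require moderate or severe diarrhea.
- Protocol 9.5.6.7 covers subjects who leave the unit early but stay in the study.
- Footnote 8 of the protocol's Table 1 generally ends weighing and grading after two consecutive negative cultures.

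**Primary proportion.** Protocol 9.7.2 asks for a "point estimate and the corresponding two-sided 95% confidence interval". SAP Table 12 notes: "N = Number of subjects in the Full Analysis Set; n = Number of subjects meeting the corresponding endpoint". SAP 3.1.1 bases percentages on the non-missing sample size. Protocol 9.7.6.2 leaves dropout handling to the SAP, and SAP 3.5 says that "no imputation will be performed for missing values".

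**The concern.** Kaplan-Meier estimation relies on each subject counting in the risk set only while an event could have been observed. The 2.5.4 rule keeps an event-free subject at risk until 120 hours even if stool observation stopped on Day 2. That is unobserved follow-up, and it can only pull the estimated cumulative incidence down.

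The two texts also lead to different outputs. One programmer working from section 2.5.4 and another from the table footnote would produce different curves and possibly different quartiles. Table 15 is marked for the topline report, and SAP 8.1 treats topline results as final, so the rule needs to be settled beforehand.

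For onset there is a further fault. If non-events leave the risk set at 120 hours but later onsets still count, the only subjects at risk after 120 hours are those who go on to have an event. A single late onset then takes the estimated cumulative incidence to 100%, whatever the true rate.

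A separate gap concerns the attack rate, the one quantity that the study exists to estimate. No available text says how an event-free subject with a truncated window is classified.

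**Working it through.** **1. The plan's own figure.** SAP 2.4.1 gives Clopper-Pearson intervals for n=25 at 60% and 72%. Exact limits from beta quantiles are 15/25: (0.387, 0.789), and 18/25: (0.506, 0.879). Both agree with the stated (0.39, 0.79) and (0.51, 0.88).

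**2. Inputs for the illustration.** N = 25 is the minimum enrollment (protocol 9.3.4), and 15 events is the 60% scenario of SAP 2.4.1. The documents give no dropout rate, so 2 event-free leavers is an assumption. Event times are also assumed: 15 log-spaced times from 7.4 to 84 hours with a median of 24.9. This is in line with the 25-hour median in protocol 7.2 and the 7-84 hour range in protocol Table 3.

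**3. Kaplan-Meier value at 120 hours.** Let d1 events occur before the leavers' exit and d2 after it, with k leavers. Between censorings the product telescopes, so

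F(120) = 1 − [(N − d1)/N] × [(N − d1 − k − d2)/(N − d1 − k)].

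With every non-event censored at 120 hours, this reduces to the crude proportion, 15/25 = 60.0%. With k = 2 censored at exit:

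| Exit | d1 | d2 | Calculation | F(120) |
|---|---|---|---|---|
| 20 h (simpler 5/10 split assumed) | 5 | 10 | 1 − (20/25)(8/18) | 64.4% |
| 24 h | 7 | 8 | 1 − (18/25)(8/16) | 64.0% |
| 48 h | 11 | 4 | 1 − (14/25)(8/12) | 62.7% |
| 72 h | 14 | 1 | 1 − (11/25)(8/9) | 60.9% |
| 96 h | 15 | 0 | after the last assumed event | 60.0% |

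For exit at 24 hours, one leaver gives 61.9% and three give 66.4%.

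**4. Effect on a quartile.** Table 15 reports quartiles. With all non-events censored at 120 hours, survival first reaches 0.5 or less at the 13th event (12/25 = 0.48), assumed at 59.4 hours. With two exits at 24 hours it does so at the 12th event (0.72 × 11/16 = 0.495), at 49.9 hours. For exits at 48 hours or later the median is unchanged. The size of this shift depends on the assumed spacing.

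**5. Primary proportion with 2 event-free leavers.**
- Counted as non-cases: 15/25 = 60% (39-79).
- Excluded: 15/23 = 65% (43-84).
- Counted as cases: 17/25 = 68% (46-85).

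Each leaver wrongly counted as a non-case lowers the rate by 1/25 = 4 points, or 1/30 = 3.3 points at n=30. A leaver who would have had no event lowers it by nothing.

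**The case against.** A reader might infer that the 120-hour censoring sentence biases the attack rate downward. The documents do not support that. The sentence governs a secondary Kaplan-Meier analysis, whereas the attack rate is a proportion of committee decisions (SAP 2.5.2, 5.1, Table 12) in which no censoring time enters.

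Nor is it stated that leavers count as confirmed non-cases. Table 12's denominator suggests it, but the non-missing rule in 3.1.1 could drop a subject with no determination, and the adjudication charter, which is not available here, may settle the matter. SAP 2.5.4.1 also says that the committee may count a subject whose measured stools fell below threshold, so an error in one direction cannot be taken for granted.

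The exposed group should be small. Discharge needs two antibiotic doses, two negative stools and improved symptoms. Routine antibiotics start on the morning of Day 6, about 120 hours after challenge. Two of the early-treatment criteria already imply the stool threshold. What remains is immediate withdrawal, or early treatment on other grounds. SAP 3.5 expects little missing data, and Table 10 already counts early terminations.

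All of this stands, and it limits the size and the wording of the point. It does not remove the contradiction between section 2.5.4 and footnote e, the mismatched windows for onset, or the absence of a stated classification rule.

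**Conclusion.** The SAP's censoring rules conflict and should be reconciled before the topline output. The 2.5.4 version is wrong for any event-free subject whose stool observation ends before 120 hours. Footnote e is closer, but discharge need not coincide with the end of weighing and grading.

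Under the assumptions above (25 subjects, 15 events, 2 leavers), the understatement of the 120-hour incidence is about 4 points for exit within the first day, 2.7 points at 48 hours and 0.9 at 72. It is zero if nobody leaves early. These differences are well inside the 39-79% interval.

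For the attack rate the conclusion is conditional: it may be understated, by at most 4 points per leaver at n=25, if event-free leavers are counted as non-cases. Whether they are is not settled by the protocol or SAP.

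Censoring at exit is not automatically unbiased. A subject who leaves after antibiotics may differ in risk from those who remain, so the bounds matter as much as the curve.

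**What to change.** 1. In SAP 2.5.4.1-2.5.4.3 and Table 15 footnote e, use one rule for all three endpoints: censor non-events at the earlier of the end of the endpoint's event window and the end of stool observation. Define the latter as the recorded date and time of leaving the unit or of stopping stool weighing and grading.
2. State where each event window ends. For onset, make the event and censoring windows the same. For the other two endpoints, note that the definitions accept a threshold stool after 120 hours if the episode began before then.
3. In Table 12, keep the FAS row as primary and state how subjects with truncated observation are classified in it. Footnote the number whose stool observation ended before 120 hours without the endpoint. If that number is not zero, add a supportive bound: such subjects excluded, and counted as cases.

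The cost is some SAP wording and at most two table rows. Exit time to the hour is needed. Listing 3 shows only study day and Listing 6 only grade 3-5 stools, so it must come from the recorded data, but footnote e already requires the discharge time.
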